## 10.6 Secondary Malignancy

A *secondary malignancy* is a cancer caused by treatment for a previous malignancy (e.g., treatment with investigational agent/intervention, radiation or chemotherapy). A secondary malignancy is not considered a metastasis of the initial neoplasm.

CTEP requires all secondary malignancies that occur following treatment with an agent under an NCI IND/IDE be reported expeditiously via CTEP-AERS. Three options are available to describe the event:

- Leukemia secondary to oncology chemotherapy (e.g., acute myelocytic leukemia [AML])
- Myelodysplastic syndrome (MDS)
- Treatment-related secondary malignancy

Any malignancy possibly related to cancer treatment (including AML/MDS) should also be reported via the routine reporting mechanisms outlined in each protocol.

## 10.7 Second Malignancy

A second malignancy is one unrelated to the treatment of a prior malignancy (and is **NOT** a metastasis from the initial malignancy). Second malignancies require **ONLY** routine AE reporting unless otherwise specified.

## 11. STUDY CALENDAR

Informed consent is to be obtained any time prior to conducting research procedures and may be greater than 14 days before Randomization. Baseline timepoint scans, Echocardiogram (or MUGA), Eye Exam, and Pre-Treatment Biopsy are highly recommended to be done within 14 days of randomization but can be done up to a maximum of 28 days prior to randomization, if needed to accommodate scheduling limitations. Screening labs must be done within 14 days of randomization. In the event that the patient's condition is deteriorating, laboratory evaluations should be repeated within 48 hours prior to initiation of the next cycle of therapy. All participants receiving atezolizumab will be assessed for pulmonary signs and symptoms on physical examination as well as imaging throughout the study.

| 1 cycle = 28 days                   | Baseline                            | Cycle 1 |        |        | Cycle 2        |        |        | Cycle 3 and beyond |       |         | Progression/
End of
Treatment s |
|-------------------------------------|-------------------------------------|---------|--------|--------|----------------|--------|--------|--------------------|-------|---------|--|
|                                     |                                     | Day 1   | Day 15 | Day 21 | Day 1          | Day 15 | Day 21 | Day 28             | Day 1 | Day 15  |  |
| Visit window t           | -Day 14
to
Randomi-
zation | +/-2    | +/-2   | +/-5   | +/-2           | +/-2   | +/-5   | +/-2               | +/-2  | +/-5    | +14  |
| Atezolizumab b           |                                     | X       | X      | X      | X              | X      | X      | X                  | X     | X       |  |
| CDX-1127 (vanilimumab) c |                                     | X       | X      | X      | X              | X      | X      | X                  | X     | X       |  |
| Cobimetinib d            |                                     | X-----X |        |        | X-----X        |        |        | X-----X            |       | X-----X |  |
| Informed consent                    | X                                   |         |        |        |                |        |        |                    |       |         |  |
| Demographics                        | X                                   |         |        |        |                |        |        |                    |       |         |  |
| Medical history e        | X                                   |         |        |        |                |        |        |                    |       |         |  |
| Concomitant medications             | X                                   | X       |        |        | X              |        |        | X                  |       |         |  |
| Physical exam f          | X                                   | X       | X      | X      | X              | X      | X      | X                  | X     | X       |  |
| Vital signs g            | X                                   | X       | X      | X      | X              | X      | X      | X                  | X     | X       |  |
| Height                              | X                                   |         |        |        |                |        |        |                    |       |         |  |
| Weight                              | X                                   | X       |        |        | X              |        |        | X                  |       |         |  |
| Performance status                  | X                                   | X       |        |        | X              |        |        | X                  |       |         |  |
| CBC w/diff h             | X                                   | X       | X      | X      | X              | X      | X      | X                  | X     | X       |  |
| Serum chemistry i        | X                                   | X       | X      | X      | X              | X      | X      | X                  | X     | X       |  |
| Amylase, Lipase                     | X                                   |         |        |        | X              |        |        | X                  |       |         |  |
| Coagulation (INR and
aPTT)       | X                                   |         |        |        | X j |        |        | X                  |       |         |  |
| Thyroid function test k  | X                                   |         |        |        | X              |        |        | X                  |       |         |  |
| EKG l                    |                                     | X       |        |        |                |        |        |                    |       |         |  |
| B-HCG m                  | X                                   |         |        |        |                |        |        |                    |       |         |  |
| CPK                                 | X                                   |         |        |        |                |        |        | X n     |       |         |  |
| cfDNA o                  | X                                   |         |        |        |                |        |        |                    |       |         |  |
| ECHO or MUGA o           | X                                   |         |        |        |                |        |        |                    |       |         |  |
| Ophthalmologic exam o    | X                                   |         |        |        |                |        |        |                    |       |         |  |
| Adverse event evaluation            |                                     | X       | X      |        | X              | X      |        | X                  | X     | X       | X w                                   |

t1 month after first dose, then every 3 mo on cobimetinib (see u)  
uEvery 2 months for 1 year, then every 6 months while on cobimetinib (see v)

| 1 cycle = 28 days                                       | Baseline   | Cycle 1             |        |        | Cycle 2 |       |        | Cycle 3 and beyond |        |       | Progression/
End of
Treatment s |
|---|--|---------------------|--------|--------|---------|-------|--------|--------------------|--------|-------|--|
|   |  | Day 1               | Day 15 | Day 21 | Day 28  | Day 1 | Day 15 | Day 21             | Day 28 | Day 1 |  |
| Visit window d                               | -Day 14
to
Randomization   | Day 0  | +/-2   | +/-2   | +/-5    | +/-2  | +/-2   | +/-5               | +/-2   | +/-2  | +/-4   |
| Tumor measurements N                         | X  |                     |        |        |         |       |        |                    |        |       |  |
| CA 19-9 o                                    | X  | X                   |        |        |         | X     |        |                    |        |       | X  |
| Archival tumor sample                                   | X  |                     |        |        |         |       |        |                    |        |       | X  |
| Tumor biopsy p                               | X  |                     |        |        |         |       |        |                    |        |       |  |
| Peripheral blood in EDTA tubes Q             | X  |                     |        |        |         |       |        |                    |        |       | X x                                   |
| Peripheral blood (Streck tube) Q             | X  |                     |        |        | X       |       |        |                    |        |       | X  |
| Peripheral blood (red top tubes for serum) R |  |                     | X      | X      |         |       | X      |                    |        |       |  |
| Medication Diary  |  |                     | X      |        |         | X     |        |                    |        |       |  |
|   | A: Longer durations to be approved by the Study Principal Investigator. Baseline timepoint scans, Echocardiogram (or MUGA), Eye Exam, and Pre-Treatment Biopsy are highly recommended to be done within 14 days of randomization but can be done up to a maximum of 28 days prior to randomization, if needed to accommodate scheduling limitations.   |                     |        |        |         |       |        |                    |        |       |  |
|   | B: To be administered to both Arm A and Arm B treatment arms. Dosing as follows: atezolizumab 840 mg IV q2wks. Atezolizumab will be administered before CDX-1127 (varilumab).  |                     |        |        |         |       |        |                    |        |       |  |
|   | C: To be administered to both Arm A and Arm B treatment arms. Dosing as follows: CDX-1127 (varilumab) 3mg/kg IV q2wks. Wait 30 minutes between completion of atezolizumab and subsequent start of CDX-1127.  |                     |        |        |         |       |        |                    |        |       |  |
|   | D: For patients randomized to atezolizumab and CDX-1127 (varilumab) plus cobimetinib ( study arm A only ). Dosing as follows: cobimetinib 60 mg daily (21 days on/7 days off). On Days 1 and 15 of each cycle, cobimetinib should be taken before receiving atezolizumab and CDX-1127 (varilumab). Cobimetinib should be taken in the morning at the same time every day. It can be taken with or without food. If a dose of cobimetinib is not taken within 4 hours of the scheduled dose, it should be considered missed and not taken. Resume dosing at the next scheduled dose/time. If unable to take dose prior to infusion, patient may still take that day's dose as long as it is within 4 hours of regularly scheduled time, otherwise it should be considered missed and not taken with dosing resumed at the next scheduled day/time. |                     |        |        |         |       |        |                    |        |       |  |
|   | E: Includes history of lung disease, HIV, hepatitis B or C infection, and complete cancer history, including primary site of cancer, gross location of primary tumor, secondary sites of cancer, histology, histologic grade, date of initial diagnosis, date of metastatic diagnosis, and prior cancer therapy regimens.  |                     |        |        |         |       |        |                    |        |       |  |
|   | F: Complete physical exam will be completed at baseline; focused physical examinations will be conducted thereafter. Physical examinations should be performed within a window of up to 7 days prior to dosing on Days 1 and 15 of Cycle 1 and Day 1 for all subsequent cycles.  |                     |        |        |         |       |        |                    |        |       |  |
|   | G: For the first infusion, the patient's vital signs (heart rate, respiratory rate, blood pressure, and temperature) should be determined within 60 minutes before, during (every 15 [±5] minutes), and 30 (±10) minutes after the infusion. For subsequent infusions, vital signs will be collected within 60 minutes before and within 30 minutes after the infusion. Vital signs should be collected during the infusion only if clinically indicated.  |                     |        |        |         |       |        |                    |        |       |  |
|   | H: Clinical hematology: CBC with differential ANC, ALC, AEC, and platelet count. Labs may be collected within a window of up to 7 days prior to Cycle 1 Day 1 dosing and up to 3 days prior to all other dosing days. Initial screening bloodwork does not need to be repeated if performed within 7 days of CD1.  |                     |        |        |         |       |        |                    |        |       |  |
|   | I: Serum Chemistry should include Glucose, Calcium, Sodium, Potassium, $\text{CO}_2$ , Chloride, BUN, Creatinine, Alkaline phosphatase (ALT), Aspartate amino transferase (AST), Bilirubin, Albumin, GGT, Total Protein, and LDH. For patients on Arm A (i.e. receiving cobimetinib), also include Phosphorus and Magnesium. Labs may be collected within a window of up to 7 days prior to Cycle 1 dosing and up to 3 days prior to all other dosing days. Initial screening bloodwork does not need to be repeated if performed within 7 days of CD1.  |                     |        |        |         |       |        |                    |        |       |  |
|   | J: Baseline thyroid testing should be done only in patients with a known history of thyroid dysfunction and/or if there is a clinical concern for thyroid dysfunction at the time of study screening. Free T3/T4 should be checked reflexively if fTSH is abnormal. Subsequent labs during treatment may be collected within a window of up to 3 days prior to dosing days.  |                     |        |        |         |       |        |                    |        |       |  |
|   | K: Serum or urine pregnancy (women of childbearing potential only) is required at baseline. For women with a mildly elevated B-HCG who in the opinion of the investigator are not pregnant, a vaginal ultrasound must be obtained to confirm that the participant is not pregnant in order to enroll on this study. Pregnancy tests during treatment as clinically indicated.  |                     |        |        |         |       |        |                    |        |       |  |

| Visit window d  | Baseline                           |                      | Cycle 1 |        |        | Cycle 2 |       |        | Cycle 3 and beyond |        |       | Progression/
End of
Treatment e |        |        |
|--|------------------------------------|----------------------|---------|--------|--------|---------|-------|--------|--------------------|--------|-------|--|--------|--------|

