#### 4.3.2 Special Instructions for Patient Enrollment

Pre-registration Step 0 and Registration Step 1 are to be performed at the same time and after patient has completed all elements of the screening and eligibility requirements and is ready to enroll/be randomized.

The Baseline Biopsy is to be conducted after Registration Step 1 is completed and prior to starting the assigned treatment regimen.

This Study will use the ETCTN Specimen Tracking System (STS).

- All biospecimens collected for this trial must be submitted using the ETCTN Specimen

Tracking System (STS) unless otherwise noted.

- The system is accessed through Rave user roles: “Rave CRA” and “Rave CRA (Labadmin)” for data entry at the treating institutions and “Biorepository” for users receiving the specimens for processing and storage at reference labs and the NCI Early-Phase and Experimental Clinical Trials Biospecimen Bank (EET Biobank, formerly known as the ETCTN Biorepository).
- Please refer to the Medidata Account Activation and Study Invitation Acceptance link on the CTSU website in the Data Management section under the Rave Home tab and then under Rave Resource Materials.
- **Important: Failure to complete required fields in STS may result in a delay in sample processing.** Any case reimbursements associated with sample submissions will not be credited if samples requiring STS submission are not logged into STS.

Detailed instructions on use of the STS can be found in Section 5.4.

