## 5.2 Summary Table(s) for Interventional Radiologist for Research Biopsies

| Biopsy #: 1  |                  |   |                        |                        |
|---|------------------|---|------------------------|------------------------|
| Trial Time Point: Baseline   |                  |   |                        |                        |
| IR Biopsy Definition: Research – No Clinical Impact (All cores from a single biopsy procedure impact research goals, but do not directly impact patient care or benefit the patient. |                  |   |                        |                        |
| Core Priority   | Use in the Trial | Biomarker Name(s)   | Tumor Content Required | Post-Biopsy Processing |
| 1   | Integrated       | CD8+T effector cells  | ≥10%                   | FFPE                   |
| 2   | Exploratory      | PD-L1 expression on tumor and tumor infiltrating lymphocytes (TILs) | ≥10%                   | FFPE                   |

|     |             |   |             |             |
|-----|-------------|---|-------------|-------------|
| 3   | Exploratory | Analysis of tumor microenvironment examining changes to focused tumor immune infiltrating lymphocyte populations by multiplex IHC | $\geq 10\%$ | FFPE        |
| 4-5 | Exploratory | Analysis of expression of immune-related pathways in the tumor microenvironment by RNA seq  | $\geq 10\%$ | Snap Frozen |

| Biopsy #: 2  |                  |   |                        |                        |
|---|------------------|---|------------------------|------------------------|
| Trial Time Point: Cycle 1, Day 21  |                  |   |                        |                        |
| IR Biopsy Definition: Research – No Clinical Impact (All cores from a single biopsy procedure impact research goals, but do not directly impact patient care or benefit the patient. |                  |   |                        |                        |
| Core Priority   | Use in the Trial | Biomarker Name(s)   | Tumor Content Required | Post-Biopsy Processing |
| 1   | Integrated       | CD8+T effector cells  | $\geq 10\%$            | FFPE                   |
| 2   | Exploratory      | PD-L1 expression on tumor and tumor infiltrating lymphocytes (TILs)   | $\geq 10\%$            | FFPE                   |

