| N: Baseline scans must be done <4 weeks prior to randomization. Tumor measurement will be performed with contrast CT chest/abdomen/pelvis. Non-contrast CT chest/abdomen/pelvis or CT Chest and MRI Abdomen/pelvis will be performed in subjects with contraindications or intolerance to contrast dye. For the first on-treatment scan, this should be done approximately 8 weeks from the start of treatment (not from the date of the pre-treatment baseline scan). Imaging will be repeated every 8 weeks, irrespective of dosing schedule or treatment delays. For the End of Treatment visit, scans do not need to be repeated if a scan has been performed within 8 weeks. For patients removed from study treatment for reasons other than progression, scans are to continue every 8 weeks until progression. |                                    |                      |         |        |        |         |       |        |                    |        |       |  |        |        |
| O: CA19-9 does not need to be repeated in the event that the screening lab draw show that the patient's tumor does not secrete CA19-9.   |                                    |                      |         |        |        |         |       |        |                    |        |       |  |        |        |
| P: Only for subjects with tumor that in the opinion of the study treatment team is safely accessible for biopsy. See Section 5.5.2 for the order of the tumor cores to be collected. The baseline biopsy is to be done after randomization but before C1D1.  |                                    |                      |         |        |        |         |       |        |                    |        |       |  |        |        |
| Q: Blood collection will be collected at baseline, C1D21, and Week 12 (end of Cycle 3). Pre-treatment baseline EDTA and Streck tube draws should only be drawn on enrolled patients and can be drawn anytime between time of enrollment and prior to start of treatment. These samples must be collected only Monday - Thursday and shipped overnight same day. See Section 5.1 for more details.  |                                    |                      |         |        |        |         |       |        |                    |        |       |  |        |        |

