| AA: Day 0 = time period after randomization up until C1D1 of treatment. Baseline research blood draws (EDTA and Streck tubes) and baseline study tissue biopsies should take place during this period (after patient has completed enrollment and prior to start of therapy).  |                                    |                      |         |        |        |         |       |        |                    |        |       |  |        |        |

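### The study calendar permits the research baseline biopsy up to 28 days before randomisation, while Section 4.3.2 and calendar footnotes P and AA place it after randomisation; the five statements need one timing.

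*Combined protocol and SAP*

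**What the plan says.** Five places in the protocol fix the timing of the baseline biopsy.

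- **Section 11, introduction.** The biopsy is grouped with the baseline scans, the cardiac function test and the eye examination: "Pre-Treatment Biopsy are highly recommended to be done within 14 days of randomization but can be done up to a maximum of 28 days". The direction of the 28 days is explicit: "can be done up to a maximum of 28 days prior to randomization, if needed to accommodate scheduling limitations".
- **Section 11, footnote A.** The same allowance is repeated: these procedures "can be done up to a maximum of 28 days prior to randomization".
- **Section 4.3.2.** "The Baseline Biopsy is to be conducted after Registration Step 1 is completed and prior to starting the assigned treatment regimen". The same section says that registration happens "after patient has completed all elements of the screening and eligibility requirements and is ready to enroll/be randomized".
- **Section 11, footnote P.** "The baseline biopsy is to be done after randomization but before C1D1".
- **Section 11, footnote AA.** This defines Day 0 as the period from randomisation to the first dose, and says that "baseline study tissue biopsies should take place during this period (after patient has completed enrollment and prior to start of therapy").

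On the purpose of the procedure, Section 5.2 says: "All cores from a single biopsy procedure impact research goals, but do not directly impact patient care or benefit the patient".

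**The concern.** The first two places allow a biopsy before randomisation and the other three do not. Footnotes A, P and AA belong to the same calendar, so a study coordinator meets both instructions in one table. Three things are at stake.

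1. **Participant burden.** Section 5.5.2 allows up to five cores, and Section 10.3.4 makes biopsy-related events such as haemorrhage and organ injury adverse events of special interest. If the biopsy follows registration, a patient who fails screening never has it. Under the 28-day allowance, that patient can.
2. **Specimen handling.** The tracking procedure assumes that the patient is already registered.
3. **The integrated biomarker.** CD8+ T-cell density is compared between arms as a change from baseline (Section 9.4), so the age of the baseline sample matters.

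**Working it through.** **Step 1: the timing rules side by side.**

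| Place | Before randomisation? | After randomisation, before first dose? |
|---|---|---|
| Section 11 introduction | Permitted, up to 28 days | Not excluded |
| Footnote A | Permitted, up to 28 days | Not excluded |
| Section 4.3.2 | No | Required |
| Footnote P | No | Required |
| Footnote AA | No | Stated as when it should take place |

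The conflict lies in the middle column. A biopsy taken there follows the first two places and departs from the other three.

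**Step 2: specimen tracking.** Section 5.4.2.2 requires tissue labels to carry the Patient Study ID, the Universal Patient ID and a specimen ID generated by Rave. Section 5.4.3.1 says that the registration system creates the two patient IDs, and that registration data reach Rave only when the final registration step ends. Section 5.4.3.2 has labels printed before the specimen is collected. By Section 4.3.2, both registration steps are done together once screening is complete. A biopsy taken before registration therefore comes before the identifiers and the Rave record that the workflow needs.

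**Step 3: interval from biopsy to first dose.** Section 4.4 asks for treatment to begin within 7 days of registration. Taking registration and randomisation as the same day:

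- biopsy after randomisation: at most about 7 days;
- biopsy under the 28-day allowance: up to 28 + 7 = 35 days.

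**Step 4: how many patients could be affected.** The enrolment tables that follow Section 9.2 reproduce their printed totals:

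- screening: 2 + 4 + 2 + 8 + 52 + 6 = 74;
- treatment: 2 + 4 + 2 + 8 + 42 + 6 = 64.

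The surplus is 74 − 64 = 10, and 10/74 = 13.5%. The text of Section 9.2 gives a screening range of 70 to 80:

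- 70 − 64 = 6, and 6/70 = 8.6%;
- 80 − 64 = 16, and 16/80 = 20%.

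This surplus is not a count of unnecessary biopsies. Section 9.2 attributes it to dropout and attrition. Section 9.1 defines the response-evaluable population as those who started therapy, so the surplus can include patients who were randomised but never dosed. They could be biopsied under either rule. To read the whole surplus as affected, every such patient would also need tumour that is safe to biopsy (footnote P) and a site that biopsied early. On the planned numbers, 6 to 16 is a ceiling, and the documents give nothing from which to derive the actual figure.

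**The case against.** **The 28-day window is a permission.** It is offered for scheduling difficulties, and the 14-day recommendation gives no direction. A biopsy between randomisation and the first dose satisfies all five places. A reader might infer that the two sets of instructions cannot both be followed; the documents do not support that, since every site has a compliant route. What stands is that the calendar expressly offers a second route which the other three places rule out.

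**Specimen tracking makes an early biopsy hard to process.** This is correct, and it lowers the chance that a screen failure is biopsied. It is also evidence that the allowance does not fit the rest of the protocol. It does not withdraw the allowance.

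**Consent comes first.** Section 11 requires consent before any research procedure, so the issue is avoidable burden and not an unconsented procedure.

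**Both timings precede dosing.** A biopsy taken before randomisation cannot depend on the arm assigned later. A reader might infer that the CD8 comparison between arms would be biased, but the documents support only added variability, of a size that they do not allow one to calculate.

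**The extreme intervals are edge cases.** The 35 days combines the latest use of an exception with a 7-day target that is itself worded as advice. A reader might also infer that the biopsy could coincide with the last chemotherapy dose, because the washout in Section 3.2.2 is 4 weeks. That needs both limits to fall on the same day, and it is not a general feature of the schedule.

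**Section 5.2 is not the only statement of purpose.** Appendix D lists possible clinical gain to the participant among the conditions for attempting a biopsy. That disagrees with Section 5.2 and does not settle the timing.

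**Conclusion.** The inconsistency is real and sits in the current text. Use of the calendar's 28-day allowance departs from Section 4.3.2 and from footnotes P and AA. It permits a research-only invasive procedure in a patient who may never be randomised, and it takes tissue before it can be labelled as the protocol requires.

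The size is limited. A reader might take 10 patients (13.5%) as the expected number of needless biopsies. The documents support that figure only as a ceiling, 6 to 16 over the stated screening range, and it assumes that all attrition occurs before randomisation, that tumour is accessible in every case, and that every site biopsies early. The longest interval to first dose is about 35 days against about 7, assuming that the 7-day start target is met and that registration and randomisation fall on the same day. The effect on CD8 is noise in the baseline. No sample size, power or error rate is involved. The point is an internal inconsistency that should be corrected.

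**What to change.** Reconcile the Section 11 introduction, footnote A, Section 4.3.2, footnote P and footnote AA so that all five give one timing for the baseline biopsy. The shortest edit is to remove the pre-treatment biopsy from the list of procedures in the 28-day sentence, in the introduction and in footnote A. Those two places would then agree with the other three and with the specimen-tracking workflow. If the sponsor wants to keep an earlier window, the other three places and the labelling procedure would have to change, including a way to identify and track tissue, and to record biopsy events, for patients who are not yet registered. The shortest edit costs calendar wording only.
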